7.2 Subject Disposition and Data Sets Analyzed

Subject disposition, randomization, study visits, and analysis sets will be listed. Additionally, the subject visits impacted by COVID-19 will be listed.

CONFIDENTIAL

Document Date: 07 Feb 2024

Page 28 of 60

ST-AD-008 version 05

Statistical Analysis Plan

Sponsor Name: Akero Therapeutics, Inc.
Sponsor Protocol ID: AK-US-001-0102

Counts and percentages of subjects who were screened (i.e. signed informed consent), discontinued early during screening (screen failures), and randomized will be summarized in total based on all screened subjects. Reasons for screen failures will also be summarized. In addition, the number of screening failures which were noted to have a COVID-19 as a contributory factor will be summarized.

Counts and percentages of subjects in each of the following disposition categories will be presented by treatment and in total based on All Randomized Subjects:

- Subjects who were randomized
- Subjects who started study drug
- Subjects who completed the treatment
- Subjects who withdrew from the treatment
- Subjects who completed the study
- Subjects who withdrew from the study

For randomized subjects who withdraw from the treatment and withdraw from the study, the primary reason for the discontinuation/withdrawal will be summarized. In addition, early discontinuation from the treatment contributed by COVID-19 and early discontinuation from the study contributed by COVID-19 will be summarized.

A summary of subject enrollment by stratification factor will also be provided by treatment group and in total for All Randomized Subjects.

Counts and percentages of subjects in each analysis population will be summarized by treatment and in total based on All Randomized Subjects.

7.3 Protocol Deviations

All protocol deviations and COVID-19 related protocol deviations will be listed.

All important protocol deviations leading to exclusion from the PPS (see Section 5.9.1) will be listed and summarized by treatment group for All Randomized Subjects.

7.4 Demographics and Other Baseline Characteristics

Demographic and baseline measurements will be listed and summarized by treatment group and in all EFX subjects and total for All Randomized Subjects.

The following demographic and baseline characteristics will be summarized:

- Age (years)
- Age categories (<65 years, ≥65 years, ≥75 years)

CONFIDENTIAL

Statistical Analysis Plan

Sponsor Name: Akero Therapeutics, Inc.
Sponsor Protocol ID: AK-US-001-0102

- Sex
- Race
- Ethnicity
- Height (cm) at Screening
- Weight (kg) at Baseline
- Body mass index (BMI) (kg/m²) at Baseline
- BMI categories at Baseline (<30 kg/m², ≥30 kg/m²)
- Waist circumference (cm) at Baseline
- Hip circumference (cm) at Baseline
- Waist-to-hip ratio at Baseline
- T2D status at Screening
- Fibrosis stage at Screening
- Statin use at baseline
- Vitamin E/ Thiazolidinedione use at baseline
- NAS and NAS components at Screening
- Median Liver Stiffness Measurement (LSM) in kiloPascals (kPa) as Evaluated by FibroScan at Screening
- Median Controlled Attenuation Parameter (CAP) at Screening
- ALT (U/L) and AST (U/L) at Baseline
- ALT and AST categories at Baseline (≤ULN, >ULN)
- Systolic blood pressure at baseline, Diastolic blood pressure at baseline, and Systolic blood pressure category at baseline (<130mmHg, ≥130mmHg)
- Fasting values of Triglyceride (mg/dL), Total Cholesterol (mg/dL), LDL-C (mg/dL), HDL-C (mg/dL), and non-HDL-C (mg/dL) at Baseline
- Endogenous FGF21 at Baseline
- Serum fibrosis biomarkers: ELF score, Pro-C3 (μg/mL), C3M, Pro-C3/C3M, NIS-4 at Baseline
- Pro-C3 categories at Baseline (<14 μg/mL, ≥14 μg/mL)
- Liver Injury Biomarkers: MELD score and CP score at Baseline
- Bone Biomarkers: P1NP and CTX-1 at Baseline

CONFIDENTIAL

Document Date: 07 Feb 2024

Page 30 of 60
ST-AD-008 version 05

Statistical Analysis Plan

Sponsor Name: Akero Therapeutics, Inc.
Sponsor Protocol ID: AK-US-001-0102

- Insulin Sensitivity and Glycemic Control Biomarkers: Hemoglobin A1c (%), Fasting values of Insulin, Blood Glucose, Adiponectin, and HOMA-IR at Baseline

Other baseline measurements, such as safety laboratory, ADA, vital signs, and ECG, will be summarized by treatment group with the post-baseline measurements.

7.4.1 Medical History

Medical history will be coded using the Medical Dictionary for Regulatory Activities (MedDRA) Version 23.1 (or a later version if updated during the study). All medical history will be listed, and the number and percentage of subjects with any medical history will be summarized for All Randomized Subjects by treatment group and in total by system organ class (SOC) and preferred term (PT).

7.4.2 Previous and Concomitant Medications

Medications received prior to or concomitantly with study drug will be coded by Fortrea using the WHODrug Dictionary Version Sep 2020 Global Dictionary Version B3 (or a later version if updated during the study) preferred terms and Anatomical Therapeutic Chemical (ATC) Classification codes.

For summary purposes, medications will be considered prior medications if they stopped prior to the first dose of study drug and concomitant medications of the randomized treatment period if they were taken at any time on or after the first dose of study drug (i.e. started prior to the first dose of study drug and were ongoing or started after the first dose of study drug) and started prior to the 30-Day follow-up visit of the randomized treatment period.

If a medication cannot be classified as "prior" or "concomitant" after applying imputation rules for missing/incomplete dates, it will be classified as concomitant.

The use of any prior medication or concomitant medication will be listed for All Randomized Subjects. Counts and percentages of subjects taking concomitant medications by therapeutic class (ATC-Level 2), chemical subgroup (ATC-Level 4), and generic term will be summarized by treatment and in total based on the Safety Set.

7.5 Measurements of study drug Compliance

Subjects who receive less than 80% of planned doses of study drug over the course of study participation are considered noncompliant. The frequency and percentage of subjects who are compliant and noncompliant will be summarized by treatment group for the Safety Set.

CONFIDENTIAL

Statistical Analysis Plan

Sponsor Name: Akero Therapeutics, Inc.
Sponsor Protocol ID: AK-US-001-0102

7.6 Efficacy

Efficacy analysis will be performed by treatment group. In addition, all EFX subjects will be combined as "All EFX" group in all histology analyses and for other efficacy parameters as appropriate.

Note that for analyses using an MMRM model, the model will first use an unstructured covariance matrix. In the event that there are convergence issues, an autoregressive heterogeneous (ARH(1)) covariance structure will be used, followed by autoregressive structure (AR(1)) if convergence issues still exist.

In addition, for analyses using the CMH test, it is noted that the CMH test statistic is not defined in the event there are no responses in one treatment arm and that there may be issues with numerical stability of the estimated odds ratio (and related statistics, e.g. p-values) in the event of few responses within a treatment arm. Therefore, the nominal p-value and corresponding population level summaries will be generated using Fisher's Exact Test on the 2x2 contingency table of an individual active treatment arm (EFX 28mg or EFX 50mg) and Placebo, and the response variable (histology response or non-response) for a given endpoint in the event that there are no responses in a treatment arm for a given population. The analysis with all EFX subjects in a given analysis population will also be generated in this case. Further, in the event of insufficient responses (e.g. less than approximately 3 responses in a given arm) to assess numerical stability of the CMH odds ratio estimate, the Fisher's Exact Test odds ratio estimate and p-value may also be summarized in order to assess the impact of limited responses on the stability of the CMH test.

7.6.1 Primary Efficacy Analysis

The primary efficacy analysis will be conducted when all the planned subjects complete the 24-Week visit. A CMH test will be used to compare the differences in proportions of subjects who achieve a ≥ 1 -stage improvement in fibrosis compared to baseline without worsening of steatohepatitis between the EFX arms and the placebo arm, adjusting for stratification factors. The analysis will be performed using the LBAS. The point estimates and 95% confidence intervals (CIs) for the differences in proportions will be calculated. The 95% CI will be constructed using the Miettinen and Nurminen method. In addition, the odds ratio and risk ratio point estimate and 95% CI will be summarized for each EFX arm compared to placebo. The Primary efficacy endpoint will be tested at Type I error rate of 0.05, two-sided without adjustment for multiplicity for the comparisons between EFX arms and the placebo arm. P-values will be presented.

CONFIDENTIAL

Statistical Analysis Plan

Sponsor Name: Akero Therapeutics, Inc.
Sponsor Protocol ID: AK-US-001-0102

The same analysis will be repeated on the PPS and FAS. For any subjects in the FAS with a missing efficacy value, the efficacy variable will be considered as non-responder.

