6.25.1. Hepatic Events Adjudication Committee

A key objective of this study is to prevent progression to cirrhosis and associated complications. Clinical events that constitute the clinical outcomes endpoint include:

- 1) Progression to cirrhosis as defined by a liver biopsy showing F4 fibrosis according to the NASH CRN classification, as assessed by the central reader.
- 2) Events of hepatic decompensation including:

- a) Clinically apparent ascites requiring treatment
- b) HE of Grade 2 or above (according to the West Haven criteria defined in [Appendix E](#)) requiring treatment
- c) Portal hypertension-related upper gastrointestinal bleeding identified by endoscopy and requiring hospitalization, including events of bleeding from esophageal varices, gastric varices, and portal hypertensive gastropathy
- 3) Liver transplantation or qualification for liver transplantation, defined as MELD score ≥ 15 (unless due to therapeutic anticoagulation) on at least 2 consecutive occasions at least 4 weeks apart
- 4) All-cause mortality

Each of the clinical events (except histologic progression to cirrhosis, all-cause mortality and liver transplantation) will require confirmation by a Hepatic Events Adjudication Committee. All deaths will be reviewed by this committee to determine if they are liver-related.

If there is clinical evidence that a subject has progressed to cirrhosis (e.g., based on the presence of new esophageal varices, changes in biomarkers [including, but not limited to, low serum albumin, high serum bilirubin, a low platelet count, prolonged INR, or elevated liver stiffness], or development of other clinical signs or symptoms of cirrhosis), the subject should undergo repeat liver biopsy for confirmation of progression to cirrhosis (F4 fibrosis as assessed by the central reader according to the NASH CRN classification) at the discretion of the principal investigator (PI).

Once the clinical event (except histological progression to cirrhosis, all-cause mortality and liver transplantation) is confirmed by the Hepatic Events Adjudication Committee, the subject will discontinue from the study. Subjects who experience histological progression to cirrhosis, all-cause mortality and liver transplantation will be discontinued from the study, but do not require confirmation from the adjudication committee prior to discontinuation.

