7.3.3.3. Liver Biopsy Analysis Set (LBAS)

The primary analysis set for histological efficacy analyses will be the Liver Biopsy Analysis Set (LBAS), which will be a subset of the FAS. It will include all FAS subjects who have the baseline and on-study liver biopsy results.

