7.5. Estimands

In line with ICH E9 (R1) addendum, 5 attributes (treatment, population, endpoint, intercurrent events, and population-level summary) have been specified to translate the primary and key secondary efficacy objectives into treatment effects that are to be estimated (estimands).

The treatment conditions of interest are EFX 28 mg administered weekly, and EFX 50 mg administered weekly, and are compared with matching placebo administered weekly.

The treatment effect is assessed by the primary histological endpoint of improvement in liver fibrosis and no worsening of steatohepatitis.

The population of subjects targeted is adults with NASH with liver fibrosis as defined by the inclusion/exclusion criteria.

Intercurrent events are handled through a composite strategy (see Table 6).

The population-level summary of the treatment effect will be quantified by comparing observed responder proportions supported by the risk ratio of investigational product compared to placebo (EFX 28 mg versus placebo or EFX 50 mg versus placebo) calculated from the odds ratio obtained through Cochran-Mantel-Haenszel (CMH) test detailed in the Statistical Analysis Plan.

Table 6. Approach for Intercurrent Events for the Primary Endpoint

Intercurrent Event	Status
Start of additional therapy with potential to impact NASH condition (i.e. rescue medication)	Subject defined as a non-responder (even if a post-treatment biopsy is available)
MELD score ≥ 15	Subject defined as a non-responder (even if a post-treatment biopsy is available)
Hepatic decompensation event	
Unscheduled biopsy showing progression to F4	Subject will be counted as a non-responder
Bariatric surgery	Subject defined as a non-responder

The estimands attributes for all secondary histological endpoints are defined in the same manner as for the primary endpoint described above.

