- q For female subjects of childbearing potential only. Serum pregnancy test at screening and urine pregnancy test at other time points.
- r Early Termination visit should occur within 5 days of discontinuation of study drug. The 30-Day Follow-Up visit should occur 30 days following the last dose of study drug received.
- s Liver Biopsy to be obtained at Early Termination only if the subject received at least 16 weeks of EFX/Placebo. MRI to be obtained \pm 5 days from the liver biopsy.
- t The screening period may be extended by 2 weeks under special circumstances with the explicit approval of the CRO Medical Monitor.

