3.4 Estimands

In line with ICH E9 (R1) addendum, five attributes (treatment, population, endpoint, intercurrent events, and population-level summary) have been specified to translate the primary efficacy objective into treatment effect that is to be estimated (estimand).

The treatment conditions of interest are EFX 28 mg administered weekly, and EFX 50 mg administered weekly, and are compared with matching placebo administered weekly in addition to standard of care.

CONFIDENTIAL

The population of subjects targeted is adults with NASH with liver fibrosis as defined by the inclusion/exclusion criteria.

The treatment effect is assessed by the primary histological endpoint of improvement in liver fibrosis and no worsening of steatohepatitis at Week 24.

Intercurrent events are handled through a composite strategy (see Table 1).

The population-level summary of the treatment effect will be quantified by comparing observed responder proportions supported by the risk ratio of each investigational product compared to placebo (EFX 28 mg versus placebo or EFX 50 mg versus placebo) calculated from the odds ratio obtained through Cochran-Mantel-Haenszel (CMH) test detailed in the Section 7.6.1.

Table 1 Approach for Intercurrent Events for the Primary Endpoint at Week 24

The estimands attributes for all secondary and exploratory histological endpoints are defined in the same manner as for the primary endpoint described above.

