5.2 Liver Biopsy Analysis Set

The primary analysis set for histological analyses will be the Liver Biopsy Analysis Set (LBAS) which will be a subset of the Full Analysis Set (FAS). It will include all FAS subjects who have baseline and on-study liver biopsy results corresponding to the appropriate time point.

Note: Week 24 and Week 96 LBAS populations may be distinct analysis populations.

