6.1 Time points and Visit Windows

Day 1 is defined as the day of first dose of study drug. Relative days after Day 1 are calculated as (assessment date – Day 1 date) + 1. Relative days prior to Day 1 are calculated as (assessment date – Day 1 date). The day prior to Day 1 is Day -1.

Scheduled visits will be assigned to analysis visits as recorded on the eCRF. Unscheduled and early termination visits completed within 21 days following the last dose of study drug will be assigned to analysis visits according to the following visit windows.

Chemistry, hematology, lipids, coagulation and markers of liver injury and function:

Analysis Visit	Target Analysis Day	Low Analysis Day	High Analysis Day
Week 1	8	5	15
Week 4	29	16	43
Week 8	57	44	71
Week 12	85	72	99
Week 16	113	100	127
Week 20	141	128	155
Week 24	169	156	183
Week 28	197	184	211
Week 32	225	212	239
Week 36	253	240	267
Week 40	281	268	295
Week 44	309	296	323
Week 48	337	324	351
Week 52	365	352	379
Week 56	393	380	421
Week 64	449	422	477
Week 72	505	478	533
Week 80	561	534	589
Week 88	617	590	645
Week 96	673	646	EOS

CONFIDENTIAL

Document Date: 07 Feb 2024

Page 22 of 60

ST-AD-008 version 05

Statistical Analysis Plan

Sponsor Name: Akero Therapeutics, Inc.
Sponsor Protocol ID: AK-US-001-0102

Markers of glycemic control, bone biomarkers and lipid metabolism biomarkers:

Analysis Visit	Target Analysis Day	Low Analysis Day	High Analysis Day
Week 4	29	16	57
Week 12	85	58	127
Week 24	169	128	197
Week 32	225	198	253
Week 40	281	254	309
Week 48	337	310	421
Week 72	505	422	589
Week 96	673	590	EOS

Serum fibrosis biomarkers:

Analysis Visit	Target Analysis Day	Low Analysis Day	High Analysis Day
Week 12	85	44	127
Week 24	169	128	253
Week 48	337	254	421
Week 72	505	422	589
Week 96	673	590	EOS

Body weight:

Analysis Visit	Target Analysis Day	Low Analysis Day	High Analysis Day
Week 1	8	5	11
Week 2	15	12	18
Week 3	22	19	25
Week 4	29	26	43
Week 8	57	44	71
Week 12	85	72	99
Week 16	113	100	127
Week 20	141	128	155
Week 24	169	156	183
Week 28	197	184	211
Week 32	225	212	239
Week 36	253	240	267
Week 40	281	268	295
Week 44	309	296	323
Week 48	337	324	351
Week 52	365	352	379
Week 56	393	380	421
Week 64	449	422	477
Week 72	505	478	533
Week 80	561	534	589

CONFIDENTIAL

Statistical Analysis Plan

Sponsor Name: Akero Therapeutics, Inc.
Sponsor Protocol ID: AK-US-001-0102

Analysis Visit	Target Analysis Day	Low Analysis Day	High Analysis Day
Week 88	617	590	645
Week 96	673	646	EOS

FibroScan examination:

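### The primary analysis set drops a composite-strategy failure who has no qualifying biopsy, although Protocol Table 6 makes that subject a non-responder

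*SAP*

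**What the plan says.** **The estimand.** SAP 3.4: "Intercurrent events are handled through a composite strategy". Protocol 7.5 says the same and lists the events in Table 6. For rescue therapy and for MELD of 15 or more, the status is "Subject defined as a non-responder (even if a post-treatment biopsy is available". An unscheduled biopsy showing F4 and bariatric surgery are also non-response. Hepatic decompensation is listed directly under MELD; its status cell is empty in the text and appears to be merged with the MELD row. Both documents define the target population by the eligibility criteria, not by having a second biopsy.

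**The analysis.** For the primary comparison, SAP 7.6.1 states "The analysis will be performed using the LBAS", and Protocol 7.7.1 also uses the LBAS. The two documents define that set differently:

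- Protocol 7.3.3.3: "It will include all FAS subjects who have the baseline and on-study liver biopsy results".
- SAP 5.2: "It will include all FAS subjects who have baseline and on-study liver biopsy results corresponding to the appropriate time point".

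**Missing biopsies.** SAP 6.2 and 7.6.1 count a missing Week 24 biopsy as non-response in the FAS. SAP 7.6.4 labels the FAS analysis of the primary endpoint a sensitivity analysis.

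**The concern.** Under a composite strategy the event itself settles the outcome. Table 6 shows this by overriding an available biopsy, so failure does not depend on histology. An analysis set that requires a biopsy reverses the order: histology first decides who is counted, and the event rule then applies only to those who remain. No visible text admits a Table 6 failure without a biopsy to the LBAS.

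The subjects affected are the clearest failures that the estimand names, and the headline analysis would treat them as if never randomised. Dropping an EFX failure flatters EFX; dropping a placebo failure works against it. The Per Protocol Set is a subset of the LBAS (SAP 5.9), so it cannot recover them.

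**Working it through.** **1. Can a Table 6 failure reach Week 24 without a qualifying biopsy?** The protocol's own rules allow it.

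- *Hepatic event before 16 weeks of dosing (main route).* Under Protocol 6.25.1, once such an event "is confirmed by the Hepatic Events Adjudication Committee, the subject will discontinue from the study". Protocol Appendix A, footnote s: "Liver Biopsy to be obtained at Early Termination only if the subject received at least 16 weeks of EFX/Placebo". No early-termination biopsy is then due, and the subject is not there for the scheduled one.
- *Early unscheduled F4 biopsy.* The SAP 6.1 liver-histology window for Week 24 is Day 113 to Day 421. (113 − 1)/7 = 16.0 weeks and (421 − 1)/7 = 60.0 weeks. F4 found before Day 113 is an on-study result, so the Protocol LBAS keeps the subject. It is not a Week 24 result, so the SAP LBAS removes the subject. The two documents differ on the primary denominator.
- *Late biopsy (narrow).* SAP 6.1: "Unscheduled and early termination visits completed within 21 days following the last dose of study drug will be assigned to analysis visits". A later unscheduled or early-termination biopsy is not assigned to Week 24.

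Rescue therapy and bariatric surgery do not end participation, so those subjects can normally be biopsied and scored. An unscheduled F4 biopsy from Day 113 to Day 421, within 21 days of the last dose, maps to Week 24 and stays in.

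**2. Size per dropped failure.** Input: 40 per arm (Protocol 5.2.2). Planning rates and power are redacted, so the plan's sample size cannot be reproduced; this point does not depend on it. With r responders and k failures dropped, the arm's rate rises by r/(40 − k) − r/40:

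| r | k = 1 | k = 2 |
|---|---|---|
| 4 | 0.26 points | 0.53 points |
| 12 | 0.77 | 1.58 |
| 18 | 1.15 | 2.37 |
| 25 | 1.60 | 3.29 |

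**3. Effect on the test.** The counts are assumed, and the CMH test is unstratified rather than the planned stratified one.

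- 18/40 vs 8/40: p = 0.0177.
- One EFX failure dropped, 18/39 vs 8/40: p = 0.0140.
- One placebo failure dropped, 18/40 vs 8/39: p = 0.0214.

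The chance that one dropped EFX failure turns p ≥ 0.05 into p < 0.05 was found by enumerating binomial outcomes for 39 EFX and 40 placebo subjects with a biopsy. Placebo response is assumed at 10%, 20% and 30%. EFX response is set to the Phase 2a values in Protocol Table 2.

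| EFX response | Placebo 10% | Placebo 20% | Placebo 30% |
|---|---|---|---|
| 6/13 = 46.2% | 0.7% | 3.5% | 1.6% |
| 8/13 = 61.5% | 0.02% | 0.2% | 0.1% |

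The Phase 2a rates come only from subjects with at least a 30% fall in liver fat (Protocol 1.4.1.3), so they are illustrative.

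**4. Frequency.** The documents give none. Ignoring dropout, the first 16 weeks hold 120 × 16/52 = 36.9 person-years. Assuming 0.5 to 4 Table 6 events that end participation per 100 person-years, 0.18 to 1.48 are expected across all three arms.

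**5. Week 96.** SAP Table 3, footnote 1, carries the intercurrent-event rules to the secondary histological endpoints. The Week 96 window opens on Day 422. In long-term follow-up, an early-termination biopsy is due only if the last one is at least 12 months old; one may also be taken for adjudication (Protocol Appendix B, footnote o). A failure can therefore again lack a qualifying biopsy. The repeat analyses, however, already count a missing result as non-response:

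| Week 96 endpoint | FAS | MFAS | Week 24 LBAS | Week 96 LBAS |
|---|---|---|---|---|
| Resolution, no worsening of fibrosis (SAP 7.6.2.1) | yes | yes | yes | subject absent |
| Fibrosis improvement, no worsening of steatohepatitis (7.6.2.2) | yes | yes | yes | subject absent |
| Fibrosis improvement alone (7.6.2.3) | yes | yes, via SAP 6.2 | not stated | subject absent |

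**The case against.** The strongest reply is that this hardly matters. Eligible subjects have F2–F3 disease with no cirrhosis or prior decompensation, so such events within 16 weeks should be rare. The FAS repeat, in SAP 7.6.1 itself, scores the same subjects as failures with the same test, and SAP 7.6.4 adds a tipping-point grid. This stands as to size. It does not remove the conflict, because the FAS result is a sensitivity analysis.

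The routes are also narrow. Protocol 6.20 stops study drug for a liver event only where the committee judges that the event warrants it, whereas 6.25.1 ends participation on confirmation. These passages should be reconciled; a subject who stays in could still be biopsied and scored. The late-biopsy route is limited because the early-termination visit is due within 5 days (Protocol 3.3).

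The body of SAP Table 1 is not visible and might state a rule for failures without a biopsy. That limits certainty about the SAP. It does not affect the conflict within the Protocol.

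A reader might go further and infer that the FAS should be the primary set because the LBAS also omits early stoppers and subjects who refuse the biopsy. The documents do not support that as a contradiction: those are not Table 6 events, both documents name the LBAS as primary for histology, and the SAP covers ordinary missing biopsies with the FAS repeat and the tipping-point grid. That choice is a trade-off, not an error.

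**Conclusion.** The conflict is real and is certain for the Protocol: Table 6 makes the event a failure, and the LBAS can remove the subject who had it. For the SAP it holds on the wording of 5.2 and 7.6.1, subject to the unseen Table 1.

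It should be fixed, but its likely effect at Week 24 is small. One dropped failure raises an arm's rate by at most about 1.6 points, assuming 40 per arm and up to 25 responders. A reader might infer a bias towards EFX or a doubtful primary result. Neither follows: the number of such subjects is unknown, the direction depends on the arm, and under the assumed rates a single dropped EFX failure changes significance at most about 3.5% of the time.

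Nor is Week 96 left without a rule. The gap there lies in the Week 96 LBAS analyses; the FAS, MFAS and, for two of the three endpoints, Week 24 LBAS repeats already count a missing result as non-response.

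**What to change.** - In Protocol 7.3.3.3 and 7.7.1 and SAP 5.2 and 7.6.1, state that any randomised subject with a Table 6 event before the Week 24 assessment enters the primary analysis as a non-responder, whether or not a qualifying biopsy exists.
- Apply the same rule to the Week 96 LBAS analyses of the histological secondary endpoints.
- Settle on one LBAS definition, since the Protocol asks for any on-study biopsy and the SAP for one at the relevant time point.

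The cost is a sentence in each place and one derivation flag. Response rates will fall slightly.

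Timing matters. SAP section 8 speaks in the past tense of subjects having stayed on their randomised dose. This suggests, but does not prove, that the Week 24 analysis came before this SAP version. If the Week 24 data are already unblinded, label the Week 24 change post hoc; the Week 96 rule can be set in advance only if those data are still blinded.
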